### **3.6 Rationale for the proposed study**

Treatment with sirolimus alone has a suppressive rather than remission inducing effect. In addition, mTORC1 inhibition by sirolimus leads to upregulation of autophagy and paradoxically increases LAM cell survival. As explained in Section 3.4, the combination of resveratrol and sirolimus is effective in blocking autophagy and inducing apoptosis of *TSC2*−/− cells, as well as reducing their survival *in vivo* with minimal effect on normal, *TSC2*-expressing cells. These pre-clinical results form the rationale for investigating the combination of resveratrol and sirolimus as a treatment option for patients with LAM and TSC. Since there is no clinical data on the adverse effect profile and effective dosing of resveratrol in patients with LAM, we plan to conduct a phase II, dose escalating, safety and efficacy study of resveratrol in combination with sirolimus with plans for a multi-center phase III study after successful completion of this project.

Home spirometry has the potential to shorten the length of monitoring time needed to determine the disease trajectory. Reliable estimates of lung function typically require multiple measurements (3 or more) obtained over a prolonged monitoring period, usually 12 months or more. We hypothesize that the trajectory of lung function decline and treatment response can be determined in a much shorter period of time using frequent home-based spirometric measurements. Our strategy of testing home spirometry in conjunction with RESULT will allow us to directly compare home spirometry to standard office-based spirometry in an ATS/ERS calibrated laboratory and with real time quality control for both home- and office-based pulmonary function studies. Our project will validate the use of home spirometry as a novel disease-monitoring tool for patients with LAM, and will help integrate home spirometry in clinical practice, and in future studies seeking to develop novel treatment approaches.

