## 6. Study Procedures and Timelines

### 6.1 Study and Timeline Overview

Patients will be identified by the medical and research staff at the LAM clinic at the University of Cincinnati Medical Center. Study staff will screen up to 60 patients over 15 months with a goal of enrolling 25 participants. Patients who meet eligibility criteria, provide informed consent and are enrolled in the study will receive instructions regarding resveratrol dosage, route and administration. An 8-week supply of resveratrol will be provided at visit 1. Patients will begin resveratrol at a starting dose of 250mg daily, and increase the dose in two increments to a maximum dose of 1000mg daily. If patients do not tolerate a certain dose of resveratrol, the dose will be reduced to the last tolerated strength. Patients will remain on the last well-tolerated dose of resveratrol for the entire study duration. Patients who are unable to tolerate the lowest dose of resveratrol will be withdrawn from study.

The patients will be given a copy of the informed consent form. Patients will be given ample time to read and discuss the consent form with the study staff. The study staff will then answer any remaining questions asked by the patients. The patients will be offered the option of signing the consent form. Those who agree to participate will undergo the remainder of screening visit.

Prior to starting study drug, pre/post bronchodilator spirometry, diffusion capacity of carbon monoxide (DLCO), and serum VEGF-D will be obtained to establish baseline values prior to study drug initiation. The best values for FEV1 and FVC obtained during the spirometry maneuvers will be used. Patients will be followed with serial spirometry and VEGF-D levels collected at the initial visit, followed by week 8, week 16 and week 24 visits. DLCO will also be obtained at the 24-week visit in addition to spirometry.

For patients who agree to the home spirometry study, we will teach them on the proper technique to perform, record and transmit home spirometry, and provide them with a home spirometer. The patients will perform their first test during the initial visit and we will use those values to compare the home spirometer values with the office-based spirometry values. After that patients will be instructed to perform home spirometry once a week as detailed in Section 5.7.

Section 6.2 provides a summary of the study timeline and procedures.

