## 6.3 Study Visits

### Screening/Initial Visit

At the screening visit, the consent form will be presented to the potential patient. If the patient is competent to understand the risks, agrees to participate and provides informed consent and HIPAA release, the patient will undergo screening. Patients will also be informed about the home spirometry portion of this study, and given the option to opt-in or opt-out of the home spirometry evaluation. Patients may enroll in the clinical trial without agreeing to participate in the home spirometry portion. During this visit, we will review the inclusion/exclusion criteria, obtain a urine pregnancy test for women of childbearing potential (defined as any fertility status other than natural or surgical menopause or post hysterectomy), and check a serum VEGF-D level (if two previous stable values post initiation of sirolimus are not drawn). The screening visit and VEGF-D testing can be accomplished either remotely or in-person. If patients meet the study inclusion criteria, the screening visit can be their initial study visit. We anticipate that in most patients the screening visit will be the initial study visit, and the following additional steps will be completed during the visit:

- Review current medications.
- Review medical history and conduct a physical examination.
- Perform spirometry with appropriate safety precautions. All spirometry tests during all visits will be performed after supervised administration of bronchodilator in the pulmonary function laboratory.
- Perform diffusion capacity (DLCO) testing. DLCO will be performed in a supervised setting in the pulmonary function laboratory.
- Obtain clinical labs including: complete blood count (CBC), comprehensive metabolic panel (CMP), lipid panel, serum VEGF-D, sirolimus level, urine pregnancy test, and urinalysis.
- Quality of life, dyspnea and fatigue assessments
- Dispense resveratrol tablets for the next 8 week supply.

- Provide a drug diary to document drug compliance. Patients will bring the drug diary at each subsequent visit
- If the patient has consented obtain a blood sample to be stored on-site for potential future use

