### 7.2 Criteria for terminating the study

Up to 25 patients will be enrolled in this study. The maximum duration of patient participation is up to 28 weeks, including a follow-up phone contact 4 weeks after the last study visit. In the event of any death, or Grade IV Serious adverse event (SAE) attributable to the study agent and unexpected, enrollment will be suspended, pending Data Safety Monitoring Board (DSMB) review.

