## 15. Statistical considerations:

*Sample size determination:* As mentioned previously, the mean serum VEGF-D level prior to treatment was approximately 2,000pg/ml in both the MILES trial (12) as well as the everolimus trial (18). In both studies, treatment with mTOR inhibitors resulted in an almost 50% reduction in the serum VEGF-D levels (12, 18). Since patients in our study will be on sirolimus prior to enrolment, we estimate that the starting serum VEGF-D level in our study will be approximately 1,000pg/ml. The largest change between serial VEGF-D levels in the placebo group of MILES was 42%. Thus, VEGF-D responders in MILES trial were conservatively defined as patients in whom serum VEGF-D decreased to a value greater than 42% from its baseline (16). Accordingly, we made our power calculations based on the ability to show a greater than or equal to 42% change in serum VEGF-D levels. Assuming the correlation between the baseline and subsequent VEGF-D levels is 0.7, a sample size of 20 subjects will provide 80% power to detect a mean VEGF-D difference from baseline to post-treatment of 420pg/ml or higher with the level of significant of 0.05 and a standard deviation of 800 for the difference. Allowing for a 20% dropout rate, we expect to recruit 25 patients for our study. Sample size calculations were done using SAS version 9.4.

*Data Analysis:* The analysis will be based on an intention to treat design. All subjects that receive study drug will be included in the safety and efficacy analysis set. The primary analysis will occur after the last enrolled participant has completed the 24-week visit. All analyses will be performed using SAS version 9.4. A p-value less than 0.05 will be considered as statistically significant.

**Specific Aim #1:** To determine if combined resveratrol and sirolimus leads to reduction in serum VEGF-D compared to VEGF-D reduction on sirolimus alone. Paired t-test will be performed to detect the difference of serum VEGF-D after 24 weeks of treatment with the serum VEGF-D prior to enrolment. The response variable VEGF-D will be measured repeatedly, at baseline and at weeks 8, 16, and 24. The change from baseline to the other study time points will indicate the treatment effect with resveratrol and sirolimus.

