**Home spirometry evaluation:** The spirometry values will be expressed as mean  $\pm$  SD. All spirometry maneuvers will be checked for acceptability and reproducibility as specified in the ATS/ERS criteria (38) by an expert pulmonary physiologist. The spirometry values obtained from maneuvers that do not satisfy the ATS/ERS criteria for acceptability will not be used in the primary analysis. If spirometric values meet the acceptability criteria but fail to satisfy the repeatability criteria, those values will be graded for quality, but will be used in the primary analysis. Overall compliance with weekly home spirometry will be recorded and reported as a percentage. Comparison of home spirometry and office-based spirometry values will be performed using the Bland-Altman method at baseline, and at each time frame that patients get an office-based spirometry (i.e. every 8 weeks). Rate of change of FEV1 (slope) over time will be calculated by using all available values (without imputations) in a linear mixed effects model after considering the correlation of the observations within each subject, and the time between measurements will be treated as a fixed effect. In order to analyze if the trends obtained from short-term follow up with frequent home spirometry correlate with overall disease trajectory, we will compare the rate of decline obtained after 8 weeks of home spirometry to the overall rate of decline obtained after 24 weeks of follow up. A similar analysis plan will be employed for serum VEGF-D, and other biomarkers. All statistical analyses for this study will be performed using SAS, version 9.4 (SAS Institute Cary NC).

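### Home-office spirometry agreement is analysed visit by visit; one repeated-measures model would be more precise and would separate a stable patient offset from visit-to-visit disagreement

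*Combined protocol and SAP*

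**What the plan says.** Section 15 (Home spirometry evaluation), repeated in the Synopsis under Data Analysis, states: "Comparison of home spirometry and office-based spirometry values will be performed using the Bland-Altman method at baseline, and at each time frame" of office spirometry, every 8 weeks. Section 6.1 has office spirometry "collected at the initial visit, followed by week 8, week 16 and week 24 visits", so there are up to four home-office pairs per patient.

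The number of patients is small. Section 7.2 says "Up to 25 patients will be enrolled in this study", and the substudy is optional: "Patients may enroll in the clinical trial without agreeing to participate in the home spirometry portion" (Section 6.3, Screening/Initial Visit). The first home test is done at the initial visit, and "we will use those values to compare the home spirometer values with the office-based spirometry values" (Section 6.1). For weeks 8, 16 and 24 no section says which weekly home reading is paired with the office test.

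Section 3.6 gives the purpose: "Our project will validate the use of home spirometry as a novel disease-monitoring tool for patients with LAM".

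Three other parts of the plan touch the same data:
- Section 15 fits a linear mixed model to the FEV1 slope, not to the home-minus-office difference.
- Secondary endpoint 13 (Section 4.2) is a correlation of home and office values and trends.
- Section 5.7 checks the repeatability of home FEV1 over the first 4 weeks, with no office comparison.

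No section specifies repeated-measures limits of agreement, or between- and within-patient variance components for the home-minus-office difference.

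**The concern.** A Bland-Altman analysis at one visit has one difference per patient. The SD of those differences combines two sources: an offset that stays with the patient (device, technique, setting) and disagreement that changes from visit to visit. When a patient is followed on the same home device, a constant offset cancels from her change. The visit-to-visit part does not. A plan that sets out to validate home spirometry for monitoring should therefore report the two parts separately, and no single-visit analysis can do so.

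Precision is also at stake. Four separate analyses on about 20 to 25 pairs give four imprecise sets of limits, although the same patients contribute at each visit and a joint analysis could use that.

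**Working it through.** **Inputs from the documents.** The Section 15 target is 20 patients with a 20% allowance for dropout: "Allowing for a 20% dropout rate, we expect to recruit 25 patients for our study". Check: 20/(1 − 0.20) = 25, which reproduces. The documents state no precision target for the agreement analysis. The post-baseline office visits are weeks 8, 16 and 24, so k = 3.

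**Assumptions.** Let ρ be the share of the home-minus-office difference variance that is a stable patient offset. The documents do not give it, so I use 0.2 to 0.8. I take n = 20 pairs per visit, although opt-in may give fewer. The total SD of the difference is set to 1, so results are in SD units.

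**1. Single-visit limit of agreement.**
SE = √(1/n + 1.96²/(2(n − 1))) = √(0.0500 + 0.1011) = 0.39 SD at n = 20. The 95% CI half-width is 1.96 × 0.389 = 0.76 SD, or 0.81 SD with the t quantile. At the maximum n = 25 it is 0.72 SD with t.

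**2. Three visits with patient as a random effect.**
Write B = 3ρ + (1 − ρ).
- Variance of the mean difference: B/(nk).
- Variance of the estimated total variance: V = 2B²/(k²(n − 1)) + ((k − 1)/k)² × 2(1 − ρ)²/(n(k − 1)).
- SE of a limit: √(B/(nk) + 1.96² × V/4).

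At ρ = 0.2: B = 1.4, B/60 = 0.0233, V = 0.0371, SE = 0.243.
At ρ = 0.8: B = 2.6, B/60 = 0.0433, V = 0.0800, SE = 0.347.
Fitting visit as a fixed effect changes 40 within-patient degrees of freedom to 38 and moves these results by less than 0.002.

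**3. Limits for a between-visit change in the home-minus-office difference:** ±1.96 × √(2(1 − ρ)).

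| ρ | SE of limit, formula | SE of limit, simulation (20,000 runs) | Limits for change |
|---|---|---|---|
| 0.2 | 0.243 | 0.241 | ±2.48 |
| 0.4 | 0.272 | 0.272 | ±2.15 |
| 0.5 | 0.289 | 0.289 | ±1.96 |
| 0.6 | 0.307 | 0.307 | ±1.75 |
| 0.8 | 0.347 | 0.344 | ±1.24 |

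Against 0.389 for a single visit, the reduction is 38% at ρ = 0.2 (1 − 0.243/0.389) and 11% at ρ = 0.8 (1 − 0.347/0.389). The per-visit limits have an expected width of ±1.96 SD in every row.

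**4. Can per-visit results show the split?** In a simulation of 25 patients and four visits (4,000 runs), ρ = 0.9 and ρ = 0.1 gave almost the same mean per-visit SD (0.985 and 0.988). The within-patient SDs were 0.315 and 0.945, a threefold difference. Per-visit SDs alone cannot distinguish the two cases.

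**5. How well can the split be estimated?** With n = 20, k = 3 and true ρ = 0.5, the ratio of between- to within-patient mean squares is 4 times an F(19, 40) variable. With ρ estimated as (ratio − 1)/(ratio + 2), its 95% sampling range is about 0.19 to 0.71. The SE of the change limits is 0.28 SD at ρ = 0.2 and 0.14 SD at ρ = 0.8.

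**The case against.** Per-visit Bland-Altman analysis is a valid choice. It does not treat repeated pairs as independent, and it assumes nothing about equal variability across visits. It serves an optional substudy of an exploratory trial, and no agreement threshold or decision depends on the limits. The text also does not forbid a pooled analysis. All of this stands, and it fixes the weight of the point: information is lost, but nothing is biased.

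A reader might infer that the plan wastes its repeated data. The documents do not support that. Section 15 uses all available readings in a mixed model for the FEV1 slope and compares 8-week with 24-week home trends, and endpoint 13 covers trends as well as absolute values. The gap is confined to agreement: a correlation does not measure it, and the Section 5.7 check uses home readings only.

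A reader might also take the limits for a change to be the monitoring quantity itself. They are not. They describe change in home minus office, so they include office measurement noise, whereas a patient monitored at home is judged on home-to-home change. They inform that use but do not replace the slope analysis or the home repeatability check.

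The size depends on an unsourced share. At 0.5 the change limits equal the per-visit limits. With a very stable offset the precision gain is small: 6% at a share of 0.9 in the calculation with 25 patients and four visits.

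Finally, the data are less ready than they look. Pairing after baseline is undefined. Section 6.3 and the Section 6.2 schedule make office spirometry post-bronchodilator, while Sections 5.7 and 8.5 state no bronchodilator for home tests. This objection stands and changes the fix.

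**Conclusion.** The point holds as a low-cost improvement. The planned limits are correct for a single reading, and it would go too far to call them wrong. They are less precise than the planned visits allow, and they leave unanswered how much of the home-office disagreement is a stable patient offset.

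With 20 patients, three post-baseline visits and an assumed between-patient share of 0.2 to 0.8, the SE of a limit falls from 0.39 SD to about 0.24-0.34 SD, or 11-38%. Limits for a between-visit change in the difference range from ±2.48 to ±1.24 SD. The per-visit ±1.96 SD could therefore understate or overstate that change, and the planned agreement analysis would not show which. The missing variance split is the stronger half of the point, because the precision gain shrinks as the offset becomes more stable.

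The result assumes similar variability across the three visits and complete pairs. Even with the better model, the split will be imprecise at about 20 patients.

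**What to change.** Add to Section 15 one linear mixed model each for home-minus-office FEV1 and FVC at weeks 8, 16 and 24, with visit fixed and patient random. Report, each with a 95% CI:
- the mean bias;
- the limits of agreement for a single reading;
- the between- and within-patient variance components;
- the limits for a between-visit change in the home-minus-office difference.

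Pre-specify the pairing, for example the acceptable weekly home reading closest in date to the office test. State that the paired office value is post-bronchodilator while no bronchodilator is stated for home tests, so the difference includes that effect as well as office measurement noise. The Synopsis, Section 6.1 and the opening of Section 8.2 also mention pre-bronchodilator spirometry, so these passages should be reconciled when the paired office value is named.

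Keep the by-visit Bland-Altman plots as description and as a check of equal variability. Keep the in-clinic baseline pair separate, as a device check.

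The cost is a short SAP addition and two model fits (FEV1 and FVC), with no new visits or measurements. The downsides are the equal-variability assumption and an imprecise variance split, which the confidence intervals will show.

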## **16. Identification and access to source data:**

### **16.1 Identifying source data**

The site PI will keep accurate records to ensure that the conduct of the study is fully documented. Data derived from source documents will be transferred to protocol-specific CRFs. The results of all clinical and clinical laboratory evaluations will be maintained in the participant's medical records or hospital database and the data will be transferred to clinical CRFs, as applicable.

### **16.2 Updating source documentation**

Documents describing the safety profile of an investigational product, such as the investigator's brochure, will be amended as needed by the investigational product manufacturer to ensure that the description of safety information adequately reflects any new clinical findings.

The site PI will provide the IRB with the most up-to-date versions of the above documents as soon as the PI becomes aware of any changes. For investigational product, the PI will confirm that there are no changes to the Investigator Brochure every 3 months.

### **16.3 Permitting access to source data**

The investigational site participating in this study (University of Cincinnati) will maintain the highest degree of confidentiality for the clinical and research information obtained from the participants in this clinical trial. Medical and research records will be maintained at the study site in the strictest confidence. However, as a part of the quality assurance and legal responsibilities of an investigator, the investigational site will permit the study monitor, authorized representatives of the IRB, the FDA, and health authorities to examine (and when required by applicable law, to copy) clinical records for the purpose of quality assurance reviews, audits, and evaluations of the study safety and progress. Unless required by the laws that permit copying of records, only the coded identity associated with documents or with other participant data may be copied (and all personally identifying information will be removed). Authorized representatives as noted above are bound to maintain the strict confidentiality of medical and research information that is linked to identify individuals.

### **16.4 Quality control and quality assurance**

The PI will keep accurate records to ensure that the conduct of the study is fully documented. The investigator will ensure that all CRFs and participant study files are legible and complete for every participant.

The PI, through the use of the DSMB, will be responsible for the regular review of the conduct of the trial, for verifying adherence to the protocol, and for confirming the completeness, consistency, and accuracy of all documented data and accuracy of source documentation verification.

When the CRFs are complete, they will be reviewed and signed by the PI. All discrepancies identified by the site monitor will be reviewed, and any resulting queries will be resolved with the site PIs and the CRFs will be amended as needed.

## **17. Ethical considerations and compliance with good clinical practice**

### **17.1 Statement of Compliance**

This study was designed to ensure the protection of subjects according to the ethical principles of the Declaration of Helsinki and amendments concerning medical research in human subjects. This clinical study will be conducted using current good clinical practice (cGCP), as delineated in ICH, Guidance for Industry: E6 Good Clinical Practice Consolidated Guidance, and according to the criteria specified in this study protocol. Before study initiation, the protocol, the informed consent documents, and the CRFs will be reviewed and approved by the DSMB, IRB, FDA, as well as any other appropriate health authorities. Any amendments to the protocol or to the consent materials will also be approved by the appropriate bodies listed above prior to implementation.

